### 3.1 APPROPRIATENESS OF MEASUREMENTS

The primary endpoints will be  $AUC_{last}$ ,  $AUC$ , and  $C_{max}$  following injection of a single dose of 0.15 U/kg SAR341402 (in the switching arm) or NovoLog (in the non-switching arm) at Week 16. As the rapid-acting insulins SAR341402 and NovoLog are used flexibly as prandial insulin at meal-times, no dosing intervals can be defined. Consequently, the primary endpoints will be  $C_{max}$ ,  $AUC_{last}$ , and  $AUC$  and not  $AUC_{tau}$  as proposed in the FDA Guidance for Interchangeability (1). Blood samples for these PK measurements will be taken for an 8-hour period, taking into account the PK profile of SAR341402 observed in the previous Phase 1 study PDY12695. In this study, a median  $T_{max}$  of approximately 1.2 hour and a mean half-life of approximately 1.2 hours were observed for SAR341402. Thus, an 8-hour sampling period is deemed appropriate to sufficiently cover (90% of AUC according to FDA guidance) individual PK profiles.

HbA1c is an index of average glucose over the preceding weeks-to-months. It is a "weighted" average of blood glucose levels during the preceding 120 days, as glucose levels in the 30 days prior to the measurement contribute substantially more to the level of HbA1c than do glucose levels 90-120 days earlier (9). HbA1c is also the most widely accepted measure of overall, long-term blood glucose control in patients with diabetes (4, 10).

HbA1c will be determined in a central laboratory blinded to study treatment. The assessment of HbA1c and insulin dose changes will support the assessment of the clinical relevance of treatment emergent AIAs and any outliers identified in the PK analysis. As the study is not powered for efficacy evaluations, the data obtained will be considered of supportive value only to the (primary) PK and (secondary) immunogenicity data obtained.

Immunogenicity analyses will include the determination of the AIA status, AIA titers, anti-insulin aspart neutralizing antibodies, and cross-reactivity with human insulin. The potential impact of AIAs on safety, particularly as related to hypersensitivity reactions and local injection site reactions will be evaluated. Anti-insulin aspart antibodies may change the PK and PD of the insulin by binding the insulin, resulting in an overall unstable glycemic control. Therefore, the potential effect of AIAs on glycemic control (HbA1c), insulin dose and hypoglycemia will also be assessed.

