##### ***Incidence of patients with at least one hypoglycemia***

- Incidence of patients with at least one hypoglycemia will be presented by treatment group for any hypoglycemia and for each hypoglycemia category (as described in [Section 2.1.5.1](#)). Non classified hypoglycemia will be displayed.
- For any hypoglycemia, severe and documented symptomatic hypoglycemia category, incidence of patients with at least one hypoglycemia will be compared for the switching arm versus the non-switching arm using a logistic regression method. The model will include fixed-effect terms for treatment group and the randomization stratum of screening HbA1c (<8%, ≥8). If the logistic model does not converge (e.g., due to sparse data), the randomization stratum may be removed from the model. Odds-ratios and 95% CIs will be displayed using forest plots.
- The number (%) of patients with at least one hypoglycemia leading to permanent IMP discontinuation will be provided by treatment group.
- Incidence of patients with at least one severe hypoglycemia with neuroglycopenic symptoms and/or SMPG <2.8 mmol/L (50 mg/dL) will be summarized.
- If the number of patients impacted by COVID-19 is sufficient, the incidence of patients with at least one hypoglycemia (any, severe, documented symptomatic) will also be

presented by subgroup of COVID-19 impact (Non-impacted, Impacted) (see definition [Section 2.2](#)) and compared between treatment groups using a similar logistic regression model as described above, with added fixed-effect terms for the subgroup and the subgroup-by-treatment interaction. Odds-ratios and 95% CIs will be presented across subgroups using forest plots. The significance level of the subgroup-by-treatment interaction will also be provided for descriptive purpose.

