#### ***Number and rate of hypoglycemia per patient-year***

- Number and rate of hypoglycemia per patient-year (computed as  $365.25 \times [\text{total number of episodes of hypoglycemia}] / [\text{total number of days exposed}]$ ) will be summarized by treatment group for any hypoglycemia and for each hypoglycemia category (as described in [Section 2.1.5.1](#)). Non classified hypoglycemia will be displayed.
- For any hypoglycemia the cumulative mean number of hypoglycemia per patient will be summarized over time using Nelson-Aalen estimates. Figures will be provided.
- For any hypoglycemia, severe and documented symptomatic hypoglycemia category, number and rate of hypoglycemia per patient-year will be compared for the switching arm versus the non-switching arm using an overdispersed Poisson regression model with a log-link function, and the logarithm of the treatment-emergent period as offset (using PROC GENMOD). The dispersion parameter will be estimated by Pearson's chi-square statistic divided by its degrees of freedom (option SCALE=PEARSON). The model will include fixed-effect terms for treatment group and the randomization stratum of screening HbA1c ( $<8\%$ ,  $\geq 8\%$ ). If a model does not converge (eg, due to sparse data), the randomization stratum may be removed from the model. Rate ratios and 95% CIs will be displayed using forest plots.
- The number of severe hypoglycemia with neuroglycopenic symptoms and/or SMPG  $<2.8$  mmol/L (50 mg/dL) per patient-year of exposure will be summarized by treatment group.

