### ***Relationship between immunogenicity endpoints and efficacy/safety assessments***

Subgroup analyses and scatterplots will be conducted to assess the relationship between immunogenicity endpoints and efficacy/safety assessments.

The following safety/efficacy assessments will be summarized by treatment-emergent AIA (Yes, No) and for each treatment group:

- Hypoglycemia (any, severe, documented symptomatic): the proportion of patients with at least one event will be compared between treatment groups using the same statistical model as described in [Section 2.4.5.1](#) for hypoglycemia subgroup analyses.
- TEAEs: descriptive statistics presented by primary SOC and PTs, showing number (%) of patients with at least one TEAE, sorted by SOC internationally agreed order and decreasing incidence of PTs according to all TEAE summary within SOC.
- Serious TEAEs: descriptive statistics by primary SOC and PTs, showing number (%) of patients sorted by SOC internationally agreed order and decreasing incidence of PTs according to all TEAE summary within SOC.
- Injection site and hypersensitivity reactions: descriptive statistics by PT, showing number (%) of patients sorted by decreasing incidence of PT in the switching group.

- Efficacy endpoint (change from baseline to Week 16 in HbA1c): descriptive statistics by visit.
- Change in daily insulin doses (basal, mealtime, total) as defined in [Section 2.4.3](#): descriptive statistics by visit.

The relationship between the AIA titer and the efficacy and safety assessments will be explored using scatter-plots of the peak AIA titer versus the parameters below for patients from the AIA population with titer available:

- Rate per year of treatment-emergent hypoglycemia during the on-treatment period (severe hypoglycemia, documented symptomatic  $< 3.0 \text{ mol/L [54 mg/dL]}$ )
- Presence/absence of treatment-emergent hypersensitivity reactions during the on-treatment period
- Presence/absence of treatment-emergent injection site reactions during the on-treatment period
- Efficacy endpoint (change from baseline to Week 16 in HbA1c)
- Change in daily insulin doses (U/kg) from baseline to Week 16

The scatterplots will also be presented separately for patients with treatment-emergent AIAs.

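### Hypoglycemia by treatment-emergent AIA status is modelled only as at least one event, yes or no; for frequent events the SAP's own rate model would be more informative

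*SAP*

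**What the plan says.** Protocol 3.1 states the purpose: "the potential effect of AIAs on glycemic control (HbA1c), insulin dose and hypoglycemia will also be assessed". Protocol Table 2 lists this among the tertiary/exploratory objectives. The same table makes the number of hypoglycemic events per participant-year a secondary safety endpoint, alongside the number of participants with at least one event.

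For the overall arm comparison, SAP 2.4.5.1 models both endpoints. The proportion with at least one event is analysed by logistic regression. The rate is analysed "using an overdispersed Poisson regression model with a log-link function, and the logarithm of the treatment-emergent period as offset". Both cover any, severe and documented symptomatic hypoglycemia, with the HbA1c stratum in the model.

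By treatment-emergent AIA status, SAP 2.4.6.1 models only the first, for the same three categories: "the proportion of patients with at least one event will be compared between treatment groups using the same statistical model". The model it points to is the subgroup logistic regression of 2.4.5.1, "with added fixed-effect terms for the subgroup and the subgroup-by-treatment interaction". The contrast is between arms within AIA status. The rate enters only as a scatterplot axis against peak titer ("Rate per year of treatment-emergent hypoglycemia during the on-treatment period"), for severe events and documented symptomatic events below 54 mg/dL. SAP 2.4.6.1 opens by declaring the immunogenicity analyses descriptive, without formal testing.

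**The concern.** Hypoglycemia is a recurrent event. The yes/no endpoint treats a participant with one episode in 16 weeks the same as one with twenty. If most participants have at least one glucose value of 70 mg/dL or below, nearly all the information lies above the cut. Protocol 3.1 gives the mechanism of interest as insulin binding that destabilises glycemic control, which would be expected to raise the number of episodes more than the chance of a first one. The logistic model also has no term for time on treatment, although SAP 1.4 allows the Week 16 visit to slip to about 24 weeks. The rate model's offset handles that.

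At stake is how much the only modelled link between antibodies and hypoglycemia can tell a reader. Protocol 3.1 asks about the effect of AIAs, yet the planned model contrasts arms and gives no AIA Yes versus No estimate on either scale.

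**Working it through.** **The plan's own figure.** There is none for this analysis. The only stated power is at least 90% for the primary PK comparison. It reproduces: with 73 per arm, log-scale SD 0.35 and limits 0.80–1.25, power is 90.3% at a true ratio of 0.95 and 91.0% at 1.05. It says nothing about hypoglycemia.

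**Inputs.** From the documents: 112 days on treatment, so 112/365.25 = 0.307 years; 184 randomized and 146 evaluable for PK. Assumed: N = 165 (midway between 146 and 184); 25% AIA-positive (41 against 124); 20 events per patient-year without AIA; negative binomial dispersion a = 1.2; true rate ratio 1.5 or 2.0.

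**Ceiling of the yes/no endpoint.** The mean count is m = 20 × 0.307 = 6.13. P(at least one event) = 1 − (1 + a·m)^(−1/a).
- AIA No: 1 − 8.36^(−0.833) = 83.0%
- AIA Yes, rate ratio 1.5 (m = 9.20): 87.4%
- AIA Yes, rate ratio 2.0 (m = 12.27): 89.9%

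Doubling the rate moves the proportion by only 7 points.

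**AIA Yes versus No, hand check at rate ratio 1.5.**
- Yes/no: pooled proportion 0.841; SE = √(0.841 × 0.159 × (1/41 + 1/124)) = 0.066; difference/SE = 0.045/0.066 = 0.68; power about 10%.
- Rate: Var(log rate ratio) = (1/9.20 + 1.2)/41 + (1/6.13 + 1.2)/124 = 0.0319 + 0.0110; SE = 0.207; ln 1.5/SE = 0.405/0.207 = 1.96; power about 50%.

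**Simulation** (gamma-Poisson counts; Pearson-scaled Poisson for the rate; two-sided 5%; range over independent runs):

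| Contrast | Rate ratio | Yes/no | Rate model |
|---|---|---|---|
| AIA Yes vs No | 1.5 | 8–9% | 54–56% |
| AIA Yes vs No | 2.0 | 15–17% | 93% |
| AIA-by-treatment interaction | 1.5 | 2–3% | 17–18% |
| AIA-by-treatment interaction | 2.0 | 3% | 42–43% |

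The interaction rows put the effect only in switching-arm AIA-positive participants. Under the null the rate test rejects in about 5%, so its gain is not inflated type I error.

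**Precision of the interaction at rate ratio 2.0** (cells of 20, 62, 21 and 62).
- Log odds scale, variance 1/(n·p·(1 − p)) per cell: 0.552 + 0.114 + 0.337 + 0.114 = 1.117; SE 1.06. The 95% CI runs a factor exp(1.96 × 1.06) ≈ 8 either way.
- Log rate scale, variance (1/m + a)/n per cell: 0.064 + 0.022 + 0.065 + 0.022 = 0.173; SE 0.416. The factor is exp(1.96 × 0.416) ≈ 2.3.

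The true effects are of similar size on the two scales (0.61 and 0.69), so the yes/no interval is much the less informative.

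**Sensitivity.** With N = 184, AIA incidence 10–30%, gamma shape 1 or 2, 5–40 events per year and rate ratio 2, yes/no power for the interaction never exceeds 16%; the rate model gives 21–80%. At 20 per year, shape 1 and 20% AIA-positive, 30% of runs had a cell in which all or none had an event, so the odds ratio could not be estimated. In a wider grid for AIA Yes versus No at N = 165 (3–40 events per year), the smallest gain was 11% against 26%.

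**Severe hypoglycemia.** At an assumed 0.3 events per year and rate ratio 2, AIA Yes versus No gives 24–28% (yes/no) against 28–30% (rate). Few participants have any event, so the two endpoints nearly coincide.

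**The case against.** The strongest reply is that the larger power figures belong to AIA Yes versus No, which the SAP does not plan. For the interaction it does fit, the rate model reaches only about 18% and 42%. That stands: the small AIA-positive group limits either model, and changing the scale does not cure it.

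Second, the analysis is tertiary and descriptive, with no decision rule, so power is a weak yardstick. That also stands, but the loss appears equally in the intervals, as the factors of 8 and 2.3 show.

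Third, a reader might infer that the SAP ignores hypoglycemia rates in relation to antibodies. It does not. It plots them against peak titer, lists hypoglycemia for participants with outlying titers, has potential effects on glycemic control adjudicated, and allows further subgroup analyses (SAP 2.4.6.1; Protocol Table 7). None of these is a prespecified rate ratio with an interval, so they narrow the gap without closing it.

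Fourth, the exposure-time point is qualitative only, because every simulated participant had 112 days. The simulations also leave out the HbA1c stratum.

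Finally, a reader might extend the criticism to the COVID-19 subgroup, which uses the same yes/no model. The documents do not support that: the subgroup is conditional on sufficient numbers and carries no antibody hypothesis, and nothing was computed for it.

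**Conclusion.** The point holds as a minor improvement for frequent events. SAP 2.4.6.1 models hypoglycemia by AIA status only as at least one event, although a better-suited model is already specified in 2.4.5.1. Under the assumed values the rate model raises power for AIA Yes versus No from 8–9% to 54–56% at a rate ratio of 1.5, and from about 16% to 93% at 2.0. For the planned interaction it goes from 2–3% to about 18%, and from 3% to 42%. The sizes rest on assumed event rate, dispersion, AIA incidence and N; the direction held across the ranges tried, except for rare events.

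Two stronger readings are not supported. One is that a finding of no association would be purely an artefact of the scale. The fair statement is that a null yes/no result would be largely uninformative for any and documented symptomatic hypoglycemia. The other is that the safety case for switching depends on this model. The overall arm comparison already uses both proportions and rates, and the AIA analysis is exploratory.

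**What to change.** In SAP 2.4.6.1, for any and documented symptomatic hypoglycemia, add the overdispersed Poisson model of 2.4.5.1 (log exposure offset, treatment, HbA1c stratum) with treatment-emergent AIA status and its interaction with treatment. Report rates per patient-year and rate ratios with 95% CIs, both between arms within AIA status and for AIA Yes versus No. Label them descriptive. AIA status arises during treatment, so the Yes versus No ratio is an association and should be described as one.

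Keep the planned proportions and scatterplots, leave severe hypoglycemia as planned, and make no change to the COVID-19 subgroup analysis.

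The cost is a sentence or two in the SAP, a further call of a model already specified on data already derived, and one extra exploratory table.

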#### **2.4.6.2 Analyses of anti-insulin aspart neutralizing antibody data**

##### ***Neutralizing antibody response***

The number and percentage of patients will be provided by treatment group for each of the following categories:

- Patients with treatment-induced NAb,
- Patients with treatment-boosted NAb,
- Patients with treatment-emergent NAb (NAb incidence),
- Patients without treatment-emergent NAb,
- Patients with pre-existing NAb or treatment-induced NAb (NAb prevalence).

For patients with treatment-induced and treatment-boosted NAbs, the peak NAb titer will be described using median, Q1 and Q3.

The number and percentage of patients with treatment-induced, treatment-boosted and treatment-emergent NAbs will also be presented by visit in each treatment group using tables and/or graphs.

A listing with inconclusive patients will be provided.

#### ***Anti-insulin aspart neutralizing antibody data by visit***

The number and percentage of patients with anti-SAR341402/NovoLog neutralizing antibody positive and negative samples will be summarized by treatment group at each visit. The number and percentage of patients with anti-SAR341402/NovoLog neutralizing antibody positive sample will be displayed graphically by visit.

The above by-visit summaries will be performed on the overall AIA population and separately for patients with treatment-emergent NAbs.

On the group of patients with anti-SAR341402/NovoLog neutralizing antibody positive sample at a given visit, anti-SAR341402/NovoLog neutralizing antibody titers will be summarized (using descriptive statistics by number (N), median, Q1, Q3, variation coefficient, minimum, maximum, geometric mean, SD, and 95% CI).

Boxplots of NAb titers will be presented at each visit.

The above by-visit summaries will be performed on the overall AIA population and separately for patients with treatment-emergent NAbs.

#### ***Subgroup analyses***

Exploratory analyses will be performed for the subgroup defined by the Anti-SAR341402/NovoLog neutralizing antibody status at baseline (Positive, Negative). Further subgroup analyses may be performed if deemed necessary for interpretation of results.

#### ***Relationship between immunogenicity endpoints and efficacy assessments***

Subgroup analyses and scatterplots will be conducted to assess the relationship between immunogenicity endpoints and efficacy assessments.

The following efficacy assessments will be summarized by treatment-emergent NAb (Yes, No) and for each treatment group:

- Efficacy endpoint (change from baseline to Week 16 in HbA1c): descriptive statistics by visit.
- Change in daily insulin doses (basal, mealtime, total) as defined in [Section 2.4.3](#): descriptive statistics by visit.

The relationship between the NAb titer and the efficacy assessments will be explored using scatter-plots of the peak NAb titer versus the parameters below for patients from the AIA population with NAb titer available:

- Efficacy endpoint (change from baseline to Week 16 in HbA1c).
- Change in daily insulin doses (U/kg) from baseline to Week 16.

The scatterplots will also be presented separately for patients with treatment-emergent NAbs.

A listing of AIA/NAb status, insulin doses, and HbA1c data will be provided for patients with treatment-emergent NAbs and HbA1c change from baseline > 1% at Week 16.

#### **2.4.7 Analyses of efficacy endpoints**

Analyses of efficacy endpoints (change in HbA1c and FPG from baseline to Week 16 as defined in the [Section 2.1.6](#)) will be descriptive with no formal statistical testing, and based on the ITT population (ie, regardless of adherence to treatment, as per definition). All post-baseline data available during the randomized period will be described.

HbA1c, FPG and change from baseline values (% for HbA1c and mmol/L and mg/dL for FPG) will be presented by visit for each treatment group, using descriptive statistics and/or graphs.

Additionally, if the number of patients impacted by COVID-19 is sufficient, efficacy endpoints will also be presented by subgroup of COVID-19 impact (Non-impacted, Impacted) (see definition [Section 2.2](#)).

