### 2.1 STUDY RATIONALE

Per FDA Guidance (1), a biological product is considered interchangeable with the reference product if the information submitted is sufficient to show that the biological product “is biosimilar to the reference product” and “can be expected to produce the same clinical result as the reference product in any given patient” and that “for a biological product that is administered more than once to an individual, the risk in terms of safety or diminished efficacy of alternating or switching between use of the biological product and the reference product is not greater than the risk of using the reference product without such alternation or switch.” Biosimilarity is generally supported by similarity in overall level of antibody produced to the proposed biosimilar and the reference product. Differences in immune responses may be detected in a switching study. Indeed, with switching between the proposed biosimilar and the reference product, repeated exposure to each product can prime the immune system to recognize subtle structural differences between products, which may theoretically increase the overall immune response. This immunologic response is highly dependent on the structural differences between the proposed interchangeable product and the comparator product and other potential differences between the products (eg, impurities).

Study EFC15178 (Gemelli X) is designed to generate data to support the argument that SAR341402 solution is interchangeable with the intended reference product, NovoLog, for the treatment of diabetes mellitus and that switching between SAR341402 solution and NovoLog will not pose an additional risk beyond that of using NovoLog alone. The study takes into consideration the general principles as delineated in Section 351(k)(4)(A) of the PHS Act (Safety standards for determining interchangeability) and FDA’s Considerations in Demonstrating Interchangeability with a Reference Product Guidance for Industry (1).

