### 3 OBJECTIVES AND ENDPOINTS

**Table 2 - Objectives and endpoints**

Objectives	Endpoints
Primary	
To demonstrate similarity in pharmacokinetics (PK) of SAR341402 and NovoLog after 4x4-week periods of alternating administration of SAR341402 and NovoLog compared to 16-week continuous use of NovoLog in participants with Type 1 diabetes mellitus (T1DM) also using insulin glargine	AUC last , AUC, and C max following injection of a predefined, fixed dose of SAR341402 or NovoLog (0.15 U/kg) at Week 16
Secondary	
To compare the effects of alternating administration of SAR341402 and NovoLog with continuous use of NovoLog on immunogenicity	Number of participants with treatment-emergent anti-Insulin aspart antibodies (AIAs) during the 16-week treatment period
To evaluate the safety of alternating administration of SAR341402 and NovoLog versus continuous use of NovoLog	Safety evaluations, which will include evaluation of the following (for the 16-week treatment period): 
 
• Number of participants with at least one hypoglycemic event 
 
- Number of hypoglycemic events per participant-year
 
- Number of participants with adverse events (AEs) (see Section 8.3)
 
 
 

To compare other PK parameters between the two treatment arms (alternating administration of SAR341402 and NovoLog and continuous use of NovoLog)	Time to C max (T max ) following injection of a predefined, fixed dose of SAR341402 or NovoLog (0.15 U/kg) at Week 16
Tertiary/exploratory	
To compare the effects of alternating administration of SAR341402 and NovoLog with continuous use of NovoLog on insulin dose	Change in Insulin dose (basal, meal-time [SAR341402 or NovoLog], total) from baseline to Week 16
To compare the effects of alternating administration of SAR341402 and NovoLog with continuous use of NovoLog on glycemic control	Change from baseline to Week 16 in HbA1c Change from baseline to Week 16 in FPG
To compare clinical effects of treatment-emergent AIAs on glycemic control, insulin dose and safety	Clinical effects of AIAs on efficacy (HbA1c), insulin dose and safety (hypoglycemia, hypersensitivity reactions, injection site reactions)

Objectives	Endpoints

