#### **2.1.6 *Efficacy endpoints***

Efficacy endpoints are tertiary/exploratory.

HbA1c and FPG are measured in a blinded fashion at a central laboratory, for scheduled (see study flowchart in Section 1.3 of the protocol) and unscheduled assessments.

In case of premature permanent IMP discontinuation, the process described in [Section 2.5.1](#) will be applied to retrieve efficacy assessments performed at the end of treatment visit (Visit 8000).

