## **2.4 STATISTICAL METHODS**

Continuous data will be summarized by treatment group (switching arm or non-switching arm) using, if not stated otherwise, the number of observations available (N), mean, SD, minimum, median, and maximum. These apply to all data, except PK data which will be described as detailed in [Section 2.5.7](#).

Categorical and ordinal data (except PK data, see [Section 2.5.7](#)) will be summarized by treatment group (switching arm or non-switching arm) using the number and percentage of patients.

In general, descriptive statistics of parameters (result and change from baseline, if applicable) by scheduled post-baseline visits will be provided on observed cases, ie, including only patients having non-missing assessments at a specific visit. All statistical analyses (descriptive statistics, plots, and statistical models) will be performed on visits defined using the reallocation algorithm of premature end of treatment provided in [Section 2.5.3](#).

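### HbA1c and FPG are summarised arm by arm, with no prespecified between-arm difference or confidence interval; an exploratory ANCOVA would supply one at almost no cost

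*SAP*

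**What the plan says.** Protocol Table 2 lists this tertiary/exploratory objective: "To compare the effects of alternating administration of SAR341402 and NovoLog with continuous use of NovoLog on glycemic control". Its endpoints are change from baseline to Week 16 in HbA1c and in FPG. SAP Section 1.2.3 repeats the objective, and SAP Section 2.1.6 confirms the rank: "Efficacy endpoints are tertiary/exploratory".

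Protocol Section 9.4.4 leaves the tertiary methods to the SAP. SAP Section 2.4.7 says that the efficacy analyses "will be descriptive with no formal statistical testing, and based on the ITT population", and that values and changes "will be presented by visit for each treatment group, using descriptive statistics and/or graphs". SAP Section 2.4 defines the default summary for continuous data as "the number of observations available (N), mean, SD, minimum, median, and maximum". That list contains no confidence interval and no between-arm contrast.

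The other HbA1c outputs are summaries by treatment-emergent AIA or NAb status, scatterplots against peak titre, listings, and a conditional COVID-19 subgroup display (SAP Sections 2.4.6.1, 2.4.6.2 and 2.4.7). None gives a between-arm estimate.

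The protocol limits what these data are for. Section 3.1 states: "As the study is not powered for efficacy evaluations, the data obtained will be considered of supportive value only".

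**The concern.** The objective is comparative, but the planned output is two columns of summaries that the reader must subtract. Three features of the documents make an estimate worth having:

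- Protocol Section 2.1 quotes an interchangeability standard that covers "the risk in terms of safety or diminished efficacy of alternating or switching".
- Protocol Section 4.2 gives the assessment of HbA1c as the reason for the 16-week duration.
- Elsewhere the SAP estimates without testing. Section 2.4.6.1 calls the immunogenicity analyses descriptive, yet gives a stratum-adjusted risk difference in AIA incidence with a 90% CI. Section 2.4.5.1 gives stratum-adjusted odds ratios and rate ratios for hypoglycaemia with 95% CIs.

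At stake is how clearly the report can say what size of HbA1c or FPG difference the data are compatible with. Two similar means shown without an interval are easily read as showing no difference.

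**Working it through.** **The plan's own figures.** The documents give no SD, margin or power for HbA1c or FPG. The only sample-size statement concerns PK: 73 evaluable per arm, log-scale SD 0.35 and at least 90% power. It reproduces: exact two one-sided tests power is 90.3% at a true ratio of 0.95 and 91.0% at 1.05. It is not in dispute.

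**Inputs.** From the documents: 184 randomised, so 92 per arm, and 73 per arm evaluable for PK, used here as a working lower number. Assumed: SD of HbA1c change 0.5 to 0.9 percentage points; 10% to 20% of the variance of change explained by baseline; baseline SD 0.8 to 1.0.

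**Unadjusted precision.** The 95% half-width is t(0.975) × SD × √(2/n).

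| SD of change | n per arm | Half-width (HbA1c points) |
|---|---|---|
| 0.5 | 92 | 1.973 × 0.5 × 0.1474 = 0.145 |
| 0.7 | 92 | 1.973 × 0.7 × 0.1474 = 0.204 |
| 0.9 | 73 | 1.977 × 0.9 × 0.1655 = 0.294 |

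If the SD were as large as 1.2 with 73 per arm, the half-width would be 0.393.

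**Gain from baseline adjustment.** The half-width is multiplied by √(1 − R²). √0.90 = 0.949 and √0.80 = 0.894, so it narrows by 5% to 11%. The 0.145 becomes 0.138 to 0.130, and the 0.294 becomes 0.279 to 0.263, a gain of roughly 0.01 to 0.03 points. As a cross-check, with equal variances and a baseline-to-Week-16 correlation ρ, the ratio of ANCOVA to change-score standard error is √((1 + ρ)/2). That is 0.866 at ρ = 0.5 and 0.949 at ρ = 0.8, a reduction of 13% to 5%.

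**Chance baseline imbalance.**
- Without stratification, the SD of the difference in baseline means would be 0.8 × √(2/92) = 0.118 to 1.0 × √(2/92) = 0.147.
- Randomisation is, however, stratified at HbA1c 8.0%. If HbA1c is normal, the cut lies near the median and screening tracks baseline closely, stratification removes 2/π of that variance. The factor is √(1 − 2/π) = 0.603, leaving 0.071 to 0.089.
- The effect on the difference in change is √R² × SD of change × √(2/92) × 0.603. This runs from 0.316 × 0.5 × 0.1474 × 0.603 = 0.014 to 0.447 × 0.9 × 0.1474 × 0.603 = 0.036 points, small beside the half-width.

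**FPG.** Assuming a residual SD of 50 to 80 mg/dL, the 95% half-width is 16.4 to 26.2 mg/dL with 73 per arm and 14.5 to 23.3 mg/dL with 92.

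**The case against.** The strongest reply is that the plan is proportionate. HbA1c and FPG are tertiary, the study is not powered for them, and Protocol Section 3.1 uses HbA1c and insulin-dose changes to judge the relevance of treatment-emergent antibodies and PK outliers. The SAP serves the antibody purpose with AIA and NAb subgroup summaries, scatterplots, listings and adjudication. The modelled comparators, AIA incidence and hypoglycaemia, are secondary endpoints. Other tertiary endpoints (treatment-induced and treatment-boosted AIAs, NAb response, insulin dose) are only described, and so is Tmax, although it is secondary and its objective is also comparative. This stands: the plan does not contradict itself, because here a comparative objective does not always bring a model.

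Three stronger readings are tempting, and the documents do not support them:

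- **That the analysis ignores baseline.** The endpoint is change from baseline (SAP Section 2.1.6). What is absent is covariate adjustment.
- **That the trial could not say what HbA1c loss its data exclude.** N, mean and SD for each arm allow a rough unadjusted interval.
- **That baseline imbalance threatens the comparison, or that the interchangeability conclusion is weakened.** Stratification already limits the imbalance, and the confirmatory claim rests on PK.

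The reply does not justify leaving out an interval. Being unpowered and supportive is a reason for no test and no margin. A prespecified interval shows how much or how little such data exclude, and it is preferable to one assembled afterwards.

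**Conclusion.** The point holds as a modest gap. The SAP prespecifies no between-arm difference, CI or baseline-adjusted estimate for HbA1c or FPG, although comparing glycaemic control between arms is a stated tertiary objective. The main gain from closing the gap is the prespecified estimate and its interval. The extra precision, about 5% to 11% on a half-width of about 0.15 to 0.29 HbA1c points, is secondary, and protection against chance imbalance is minor. All these sizes rest on assumed SDs and variance explained. The primary PK conclusion, the sample size and the type I error are unaffected. Priority is low.

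**What to change.** Add to SAP Section 2.4.7 an exploratory ANCOVA of change to Week 16, for HbA1c and separately for FPG, with terms for arm, randomisation stratum and the continuous baseline value. Report the LS mean difference (switching minus non-switching) with its 95% CI, and state that no test or margin applies.

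Run it in the ITT population on observed Week 16 values regardless of adherence, as SAP Sections 2.1.6 and 2.4 already imply, with Week 16 assigned by the SAP's own visit allocation (Section 2.5.3). Include the delayed end-of-treatment assessments that SAP Section 1.4 admits to the analyses, up to about 24 weeks after randomisation. Report the number with a missing Week 16 value in each arm.

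The cost is two standard models on data already collected, with no new visits, samples or patients.
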